18.4.1 Stopping criteria

The study will be terminated if:

- One or more subjects experience any drug related SAEs or 2 or more subjects experience severe or clinically significant AEs considered to be at least possibly related to the FLU-v-004 therapy.
- One or more subjects experience any severe or clinically significant illness from Influenza inoculation.

The PI and the SME will perform safety reviews on available clinical and virology data as appropriate during the quarantine period.

Three clinical scenarios relating to the incidence of AEs and SAEs during the study and the procedures that should be performed in each case are presented in Table 18-1: Study stopping criteria.

Table 18-1: Study stopping criteria

Status	Criterion	Procedure
1	A report has been received of one (or more) IMP-related SAEs in any one (or more) subject(s).	If such a status occurs at any point during the study then further administration of IMP will not take place and the PI and the SME will review the data and make decisions on study continuation or termination. Subject follow-up should continue until resolution or stabilisation of AEs.
2	No IMP-related SAEs have been reported but an overall pattern of clinical changes or symptoms exists, attributed to the IMP, which may appear minor or moderate in terms of individual AEs but which collectively represent a concern for safety.	If such a status occurs at any point during the study then the PI and the SME will review the data and make a decision on study continuation or termination. Subject follow-up should continue until resolution or stabilisation of AEs.
3	Virus-related SAEs or virus-related AEs of clinical concern have been reported following Human Viral Challenge.	Subject follow-up should continue until resolution or stabilisation of all such AEs and final follow-up on Day 28 (± 5 d).

In any event, subject follow-up should continue until resolution or stabilisation of AEs and final follow-up on Day 63 (± 5 d). The exception to this would be suspension of the study for an USM (Section 18.2.2).

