STATISTICS	
The hypothesis is that vaccination with 1 dose or two doses of FLU-v + adjuvant will significantly reduce MMID when compared to individuals vaccinated with placebo.
 
The primary objective of this study is to examine whether there is a difference in the MMID post inoculation rates between either of the 2 FLU-v arms and placebo. A sample size of 41 subjects per arm (total 123) will provide 80% power to detect a difference in MMID rates of 0.70 versus 0.40 (ie difference of 0.30) using a one sided 0.05 significance level.
 
In this study, the main comparisons are for each of the FLU-v dose groups to placebo. The study will also compare the two FLU-v dosing arms but the study will not have adequate power to detect a significant difference in MMID rates at the predicted treatment rates. This study does not control for multiple comparisons since we are trying to maintain a small sample size but have high power to detect the predefined primary objective of efficacy versus placebo when FLU-v is truly beneficial. All comparisons will be made at the one sided 0.05 significance level.
 
FLU-v Statistical Analysis Plan
 
MMID rates in the 2 FLU-v groups and placebo group will be compared using a Fishers exact test. 95% confidence intervals around the difference in rates between the FLU-v groups will be presented. Adverse event rates between groups will also be compared using Fishers exact test. The secondary endpoints will be examined by calculating the median and interquartile range

SYNOPSIS	
	and then performing a two-sided Wilcoxon Rank Sum Test at the 0.05 significance level.
STOPPING CRITERIA	
The study will be terminated if:
 
• One or more subjects experience a vaccine related SAE or two or more subjects experience severe or clinically significant AEs within same organ class and confirmed by repeat sample if considered to be at least possibly related to the FLU-v vaccine.• One or more subjects experience any severe clinically significant illness from influenza challenge.

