9.2 Vaccination Phase

9.2.1 Visit 2 - Day -43

The first vaccine or placebo administration will take place on Day -43, 43 days prior to virus challenge. Study procedures will be conducted as detailed on the Time and Events, table 9.2

Once it is determined that the participant still meets Inclusion/Exclusion criteria for the research study, participants will receive the first of two injections of FLU-v 500mcg+adjuvant 2 doses, FLU-v 500mcg 1 dose + 1 dose placebo , or 2 doses of placebo. The study team will thoroughly discuss the consent with the volunteer. The study team will issue and explain the completion of self-reported adverse events in a 21-day diary card. This diary card will be used to record vaccine-related local and systemic events post first vaccination.

9.2.2 Visit 3 - Day -22 (minimum 21 days post first vaccination +7 days)

The second study drug administration will take place if the participant continues to meet all inclusion and none of the exclusion criteria. Study procedures will be conducted as detailed on the Time and Events schedule

The study team will issue and explain the completion of self-reported adverse events in a 21-day diary card. This diary card will be used to record vaccine-related local and systemic events post second vaccination.

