9.3 Quarantine and Challenge

9.3.1 Visit 4 - Admission (Day -2 or Day -1 up to 40 days post second vaccination)

Subjects will be admitted to the Quarantine unit on day -2 or day -1 (minimum 20 days post second vaccination). If subject is not available to attend admission on the Day -2/Day -1 due date, the visit can be scheduled up to 40 days post second vaccination.

The admission procedures/assessments and testing will be performed after admission and before challenge virus administration. Study procedures will be conducted as detailed on the Time and Events schedule

As determined by the PI, results of standard procedures performed in the process of admission to the Quarantine unit may be used to determine suitability, including but not limited to vital signs, height, weight, etc. They can also be used to extend eligibility beyond 90 days from

screening if the participant has been vaccinated but his admission has fallen out of the 90 days window. A Viral Challenge serology test can be repeated if required before Quarantine if the participant has been vaccinated but the admission date has fallen out of the 90 days window. However, the serology test and result must be dated within 90 days of Day 0.

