15.2.2 IMP related adverse events symptoms

Following vaccination with IMP, diary card symptoms are not reported as individual adverse events unless they are deemed to be clinically significant (i.e. progress past 7 days) in the opinion of the investigator and / or SME.

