15.2.8 Laboratory values

Deterioration in a laboratory value (compared to baseline) should only be reported as an AE if the deterioration fulfils the criteria for an AE and it is clinically significant in the opinion of the

Investigator. If deterioration in a laboratory result is associated with clinical signs and symptoms, the sign or symptom will be reported as an AE and the associated laboratory result will be considered as additional information.

The Investigator will judge whether abnormal laboratory values are clinically significant or not clinically significant, and record this in the source document. This entry should be signed and dated by the relevant investigator. Laboratory abnormalities detected at screening will be considered as part of the medical history and will not be reported as AEs.

Challenge Virus associated laboratory abnormalities (e.g., elevated ALT, AST or GGT; decreased neutrophils) may be recorded as AEs (at the discretion of the Investigator).

Any laboratory abnormality that meet the criteria of a Grade 2 AE or above will be discussed with the SME. If a Grade 3 laboratory abnormality occurs (not related to Viral Challenge), a confirmatory test should be performed, preferably within 48 hours (if practically feasible) after the results have become available.

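### The protocol's stopping rules are inconsistent: Table 18-1 does not order the terminations that the synopsis and Section 18.4.1 require, and two trigger thresholds differ between synopsis and body

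*Protocol*

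**What the plan says.** The protocol states its stopping criteria in three places: the synopsis, the two bullets of Section 18.4.1, and Table 18-1 inside 18.4.1. Section 15.4.2 refers to the last two.

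- **One IMP-related SAE.** The synopsis terminates the study if "One or more subjects experience a vaccine related SAE". The first bullet of 18.4.1 terminates it if "One or more subjects experience any drug related SAEs or 2 or more subjects experience severe or clinically significant AEs", the AEs being at least possibly related to FLU-v. For the same SAE, status 1 of Table 18-1 says that "further administration of IMP will not take place and the PI and the SME will review the data and make decisions on study continuation", with termination as the other option.
- **Two related AEs.** The synopsis version is "two or more subjects experience severe or clinically significant AEs within same organ class and confirmed by repeat sample", again at least possibly related. The 18.4.1 bullet has no organ-class or repeat-sample condition. Table 18-1 has no row for this trigger. Its status 2 covers something else: a pattern of individually minor or moderate events, referred for review.
- **Illness from challenge.** The synopsis trigger is illness that is severe and clinically significant, with no conjunction between the adjectives. The second bullet of 18.4.1 puts an "or" between them. Section 15.4.2 says that an SAE caused by the challenge agent meets the stopping criteria, and calls for both Table 18-1 and the early-termination procedure. The matching row, status 3, lists only continued follow-up to Day 28.

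**The concern.** The trial deliberately infects healthy volunteers. A stopping rule fixed in advance exists so that a defined event has a defined consequence, without relying on judgement under pressure. Here someone reading the synopsis and someone reading Table 18-1 could act differently on the same event. The difference matters most for subjects who have had their last injection and are waiting for challenge. A halt to IMP dosing does nothing for them, because the exposure still to come is the live virus.

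**Working it through.** The documents give no operating figures for these rules, so there is none to reproduce. The check is a side-by-side reading.

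| Event | Synopsis | 18.4.1 bullets | Table 18-1 | Relation |
|---|---|---|---|---|
| One IMP-related SAE | Terminate | Terminate | Status 1: stop IMP; PI and SME decide on continuation | Conflict |
| Two related severe or clinically significant AEs | Terminate, if same organ class and repeat sample | Terminate, no added condition | No row | Nested thresholds; omission |
| Illness from challenge | Terminate, if severe and clinically significant | Terminate, if either | Status 3: follow-up only | Nested thresholds; incomplete row |

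**One SAE.** Mandatory termination leaves no continuation decision to make; status 1 makes one. Its only automatic step is to stop IMP. The second dose is nominally on Day -22 and challenge on Day 0, a gap of 22 days. Section 9.3.1 sets admission at least 20 days after dose 2 and adds that "the visit can be scheduled up to 40 days post second vaccination". Inoculation follows admission by 1 or 2 days, so the gap runs from 20 + 1 = 21 to 40 + 2 = 42 days. In that interval status 1 orders nothing that protects the subject while the review is pending.

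**Two AEs.** Suppose one subject has injection-site swelling and another has nausea. Section 15.2.2 says that "diary card symptoms are not reported as individual adverse events unless they are deemed to be clinically significant (i.e. progress past 7 days"; the investigator or the SME makes that judgement. Suppose both events pass 7 days and are judged clinically significant and possibly related. The 18.4.1 bullet is met. The synopsis rule is not, because the organ classes differ. Symptoms also have no sample to repeat. The reverse cannot happen: whatever meets the synopsis rule also meets the bullet.

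How much the threshold matters can only be illustrated, because the documents give no rate for qualifying events. The nearest is one of 16 FLU-v recipients in FLU-v-002 who had an injection-site lump removed, but injection site and volume have since changed. Take N = 123 × 2/3 = 82 FLU-v recipients and an assumed per-subject event rate p.

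- Bullet: P = 1 − (1−p)^N − N·p·(1−p)^(N−1). At p = 2%: 1 − 0.191 − 0.319 = 0.49.
- Synopsis, with K = 5 equally likely organ classes treated as independent and the repeat-sample condition ignored: per class, p/K = 0.4% gives 1 − 0.720 − 0.237 = 0.043; overall, 1 − (1 − 0.043)^5 = 0.20.

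| Assumed p | Bullet | Synopsis, K = 5 | Synopsis, K = 3 to 10 |
|---|---|---|---|
| 1% | 0.20 | 0.06 | 0.09 to 0.03 |
| 2% | 0.49 | 0.20 | 0.28 to 0.11 |
| 5% | 0.92 | 0.67 | 0.78 to 0.48 |

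Relatedness is judged blind, so placebo events could count too. With N = 123 and p = 2% the pair is 0.71 and 0.37 (K = 5).

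**Illness from challenge.** For a challenge-agent SAE, 18.4.1 and 15.4.2 agree on termination. Status 3, the row to which 15.4.2 leads, has no halt, review or termination step. The "or" in 18.4.1 also matters in itself. Mild to moderate disease is the intended result of challenge, so a clinically significant but not severe illness would end the study under 18.4.1 and not under the synopsis.

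**The case against.** The strongest reply is that the rules can be followed together. The synopsis and bullets say the study ends if an event occurs, not only if. Stopping IMP, holding the review and then terminating would comply with every text on an SAE. Terminating after two AEs in different organ classes breaches nothing, because the synopsis rule is simply not triggered. On challenge illness, 15.4.2 supplies the termination step that status 3 lacks. Status 3 also covers a wider class, virus-related AEs of clinical concern, so it could not order termination for every entry.

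Other protections exist. The sponsor, SME or investigator may stop the study at any time, and the MHRA or REC may initiate termination (18.4). Urgent safety measures are available (18.2.2). A physician checks each subject's suitability on Day -22, at admission and on Day 0 (7.4.2), and eligibility is confirmed before inoculation (9.3.2).

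Much of this stands. A reader might infer that the texts on two AEs contradict each other; they do not, because one threshold lies inside the other. A reader might also infer that status 3 overrides termination, and 15.4.2 shows otherwise. Nor does the share of the calendar between dose 2 and challenge measure risk: it describes one subject's schedule, not how often the texts diverge. Day 28 in status 3 is clerical, since the sentence below the table already sets final follow-up at Day 63.

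What does not fall away is status 1, which grants a discretion that the synopsis and bullet both remove. The stop powers are discretionary, and the suitability checks concern the individual subject; neither settles whether the study ends.

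**Conclusion.** The inconsistency is real and sits in current protocol text. It comprises one conflict (discretion against mandatory termination after one IMP-related SAE), two mismatched thresholds (two related AEs; illness from challenge), one missing row and one incomplete row. The triggers need only one, two and one subjects respectively. Following status 1 or status 3 literally could let inoculation continue after an event that the protocol elsewhere says ends the study.

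This rests on reading the table as written and on taking the synopsis's paired adjectives as joint conditions. The trigger probabilities rest on assumed rates and organ-class splits. They show that the two AE thresholds differ materially, not how likely a stop was.

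It would be too strong to conclude that Part A subjects can still be protected by an amendment. SAP 5.8 describes inoculations as past events. The table footnote in SAP Section 8 says that the per-protocol and ITT populations differ by one subject, and ITT membership requires challenge. Part A challenge therefore appears complete. Alpha, power and sample size are unaffected.

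**What to change.** Amend status 1 of Table 18-1, and status 3 for events meeting the second 18.4.1 bullet, to require an immediate halt to both IMP dosing and challenge inoculation, followed by the termination that the bullets require. The PI and SME review may inform that step but not replace it.

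For the two-AE trigger and for the "or" in the challenge-illness trigger, the sponsor's safety physician should choose one threshold and use it identically in the synopsis, 18.4.1 and Table 18-1, adding the missing two-AE row. The choice should weigh that the broader bullet is more likely to end the trial. If the repeat-sample condition is kept, limit it to laboratory abnormalities. Section 15.2.8 is a model: "If a Grade 3 laboratory abnormality occurs (not related to Viral Challenge), a confirmatory test should be performed, preferably within 48 hours". Align 15.4.2 with the result and change Day 28 to Day 63.

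Since Part A challenge appears complete, the study report should state which version of each rule was applied, and the text should be settled before any Part B is added.

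The cost is amendment text, with no new assessments. Because it bears on subject safety and trial conduct, it is probably a substantial amendment under 18.2.1, needing MHRA and REC approval. Part B would need one in any case.

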15.4.2 Adverse reactions to non-IMPs

A SAE caused by a non-IMP would meet the stopping criteria for the study (Section 18.4.1). In such a case Table 18.1 and the procedure for early termination should be followed in line with Section 18.4.1)

A SAE caused by the Challenge agent would meet the stopping criteria for the study (Section 18.4.1). In such a case Table 18.1 and the procedure for early termination should be followed in line with Section 18.4.1.

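### The synopsis, section 18.4.1 and Table 18-1 of the protocol give different stopping rules for three kinds of safety event

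*Protocol*

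**What the plan says.** **Section 18.4.1, opening list.** Termination is mandatory for one or more drug-related SAEs, or when "2 or more subjects experience severe or clinically significant AEs considered to be at least possibly related to the FLU-v-004 therapy". It is also mandatory in this case: "One or more subjects experience any severe or clinically significant illness from Influenza inoculation".

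**Synopsis, stopping criteria.** Termination is again mandatory, and again one vaccine-related SAE is enough. The two-subject rule uses the same pairing of severe or clinically significant events, but adds two conditions: same organ class, and confirmation by repeat sample. The challenge-illness rule puts severe directly before clinically significant with no 'or' between them, so both appear to be required.

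**Table 18-1, in section 18.4.1.**
- Status 1, an IMP-related SAE: dosing stops, and "the PI and the SME will review the data and make decisions on study continuation or termination".
- Status 2, no IMP-related SAE but an overall pattern of changes attributed to the IMP, "which may appear minor or moderate in terms of individual AEs but which collectively represent a concern for safety": the PI and SME decide whether the study continues.
- Status 3: "Virus-related SAEs or virus-related AEs of clinical concern have been reported following Human Viral Challenge". The procedure column says only: "Subject follow-up should continue until resolution or stabilisation of all such AEs and final follow-up on Day 28".
- Line below the table: "In any event, subject follow-up should continue until resolution or stabilisation of AEs and final follow-up on Day 63".

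**Section 15.4.2.** "A SAE caused by the Challenge agent would meet the stopping criteria for the study (Section 18.4.1"). It then directs the reader to follow both Table 18.1 and the early termination procedure.

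**The concern.** Healthy volunteers are given an adjuvanted vaccine and then a live influenza virus. Section 10.1 says that clinical trials so far have given only a single dose of FLU-v, so the two-dose arm is new. When a safety event occurs, the site needs to know whether the study ends, whether dosing is held pending a decision, or whether only follow-up is required. For three kinds of event the answer depends on which part of the protocol is opened.

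The error can go either way. Following the synopsis could let the study continue after an event that section 18.4.1 treats as terminating. Following 18.4.1 could end it on an event that the synopsis would let pass. Either course could afterwards be called a departure from the protocol.

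**Working it through.** The documents give no operating characteristics for the stopping rules, so there is no figure to reproduce. The check is to take each event and read off the action under each text.

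| Event | Synopsis | 18.4.1 list | Table 18-1 |
|---|---|---|---|
| A. One IMP-related SAE | Terminate | Terminate | Status 1: stop dosing, PI and SME decide |
| B. Two subjects with severe or clinically significant, at least possibly related AEs, in different organ classes or without a confirming repeat sample | Not met | Terminate | No row for a two-subject count |
| C. One challenge illness, clinically significant but not severe | Not met | Terminate | Status 3: follow-up, silent on stopping |

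**Event A.** The synopsis and the 18.4.1 list agree with each other. The conflict is with Status 1. If termination is mandatory, the PI and SME have no decision on continuation to make; if they do have one, termination is not mandatory.

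**Event B.** The conflict is between the synopsis and the 18.4.1 list. Both admit events that are clinically significant without being severe, so they do not differ on severity. They differ on the two added conditions, which appear only in the synopsis. The second is also unclear in scope: a repeat sample makes sense for a laboratory value, but an injection-site reaction has no obvious sample, and the protocol does not say how the condition applies to one.

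**Event C.** The conflict is again between the synopsis and the 18.4.1 list, and turns on one missing word. Severity is defined on its own in section 15.3.2 (Grade 3 in Table 15-1), so an illness can be clinically significant without being severe. 18.4.1 is met by either attribute; the synopsis, as worded, needs both.

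**Virus-related SAE.** Section 15.4.2 says this event meets the stopping criteria and calls for the table and the early termination procedure together. Status 3 names the event but contains no stopping or review step, so the row is incomplete beside the section that refers to it.

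**Follow-up day.** Status 3 ends follow-up at Day 28. The scheduled follow-up visits are Day 35 and Day 63 (section 9.4 and Table 9-2), and the line below the table uses Day 63. There is no Day 28 visit.

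**Which text should be the default.** Section 15.3.2 separates severe, which describes intensity, from serious, which describes outcome. A challenge-virus SAE could therefore be serious without being severe. Under the synopsis wording it would miss the challenge-illness trigger, contrary to 15.4.2. Under 18.4.1 it would be caught as clinically significant. The 18.4.1 wording is thus the one consistent with 15.4.2, and it is the more protective.

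**The case against.** The strongest reply is that these are drafting differences with adequate cover. The synopsis is a summary, 18.4.1 introduces the table as the procedure for its scenarios, and section 18.4 lets the sponsor, the SME or the investigator stop the study at any time on safety grounds. The missing 'or' may be a slip.

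Part of this stands. Oversight is not absent, and the power to stop is broad. But a power to stop does not cancel a mandatory stop, and it does not say which text binds. The documents give no order of precedence between synopsis and body. The two added conditions in the synopsis change the rule and cannot be read as abbreviation. If the missing word is a slip, it still needs correcting.

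Four stronger readings are tempting, and the documents do not support them.

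- *A virus-related SAE leaves the site with no defined decision.* That follows only if Status 3 is read alone. Section 15.4.2 requires the early termination procedure as well, and the line below the table overrides Day 28.
- *Status 2 contradicts the two-subject rule.* It does not. It concerns an overall pattern, has no subject count, and is a separate trigger.
- *The 18.4.1 threshold is itself a fault because mild events can end the trial.* The synopsis vaccine rule also admits non-severe events, and a low threshold is a legitimate precaution here. Section 15.2.2 does gloss clinically significant diary symptoms by duration beyond 7 days, but that is an AE-reporting rule which 18.4.1 does not cite, and it still depends on the investigator's judgement.
- *The difference in the chance of stopping can be stated as a percentage.* The documents give no rate of clinically significant, possibly related events. Any figure would rest on an assumed rate and an assumed spread over organ classes, and would need a model for the repeat-sample condition.

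**Conclusion.** The stopping rules are wrong as written. There are three conflicts of decision: termination against a PI and SME decision for one IMP-related SAE; the organ-class and repeat-sample conditions for the two-subject rule; and the severity wording for challenge illness. In addition, one table row lacks the stopping step that section 15.4.2 calls for and carries a follow-up day that matches no visit.

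The conclusion rests on the current text alone and on no assumed event rate. It assumes that the synopsis means what it says on challenge illness; if an 'or' was dropped by accident, the third conflict reduces to a correction of the synopsis. It does not imply that safety oversight is missing or that either threshold is unsound. The point matters because the wording decides whether a trial in healthy volunteers stops.

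**What to change.** 1. Use one text in the synopsis and 18.4.1. Take the 18.4.1 wording by default, for both the vaccine and the challenge bullets.
2. If the sponsor wants the organ-class and repeat-sample conditions, put them in both places and limit the repeat sample to laboratory or other repeatable measures.
3. For one IMP-related SAE, choose either automatic termination or a mandatory halt to dosing pending a PI and SME decision. State that choice identically in the synopsis, the 18.4.1 list and Status 1.
4. Add to Status 3 the stopping step that 15.4.2 requires for a virus-related SAE.
5. Change Day 28 in Status 3 to Day 63.

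The cost is a protocol amendment, probably a substantial one under section 18.2.1 because it bears on subject safety, with MHRA and REC approval. No visits, samples or staff are added. Taking 18.4.1 as the default has a price: events that the synopsis would have let pass would then require termination. The sponsor may prefer otherwise for the vaccine rule, provided all the texts agree. For challenge illness, the synopsis wording would also have to be reconciled with 15.4.2.
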